8.3. Clinical Laboratory Analyses

Laboratory evaluations including the analyses of chemistry laboratory tests, hematology laboratory tests, urinalysis, and liver function tests will be based on GSK Core Data Standards.

For adults, laboratory abnormalities will be graded according to the modified DMID criteria [DMID, 2007a]. For adolescent participants over 12 years of age and less than 18 years of age, the adult DMID will be applied for all laboratory parameters with the exception of serum creatinine, which will be programmatically graded according to the modified DMID criteria for pediatric participants [DMID, 2007b].

Summaries of change from baseline values over time for clinical chemistry and hematology tests will be provided in separate tables. The frequency of laboratory abnormality events along with the shift from baseline to the worst-case post baseline value will also be provided.

Abnormal liver chemistry results will be summarized by increasing folds above the upper limit of normal (ULN) including tests of interest and thresholds as follows:

- ALT or AST > 3xULN and Total Bilirubin > 2xULN
- ALT or AST > 3xULN and ALP < 2xULN and Total Bilirubin \geq 2xULN
- ALT or AST > 3xULN and Total Bilirubin > 1.5xULN
- ALT or AST > 3xULN and INR > 1.5xULN
- $(\text{ALT}/\text{ALT ULN})/(\text{ALP}/\text{ALP ULN}) > 5$ and ALT > 3xULN *
- ALT or AST \geq 20xULN
- ALT or AST \geq 10xULN
- ALT or AST \geq 8xULN
- ALT or AST \geq 5xULN
- ALT or AST \geq 3xULN
- ALT \geq 20xULN
- ALT \geq 10xULN
- ALT \geq 8xULN
- ALT \geq 5xULN
- ALT \geq 3xULN
- AST \geq 20xULN
- AST \geq 10xULN
- AST \geq 8xULN
- AST \geq 5xULN
- AST \geq 3xULN
- Total Bilirubin > 2xULN
- Total Bilirubin > 1.5xULN

*: sign of hepatocellular injury, ALT and ALP values must occur on the same day.

In addition, graphical summary of liver function test as described below will be presented.

- Scatterplot of maximum post-baseline ALT against baseline ALT by treatment group
- Scatterplot of maximum total bilirubin value post baseline against maximum post-baseline ALT by treatment group
- Participant profiles of ALT, AST, ALP and total bilirubin

If liver events are reported in the study, listings of liver event assessment, liver biopsy details and liver imaging details will be provided. Urinalysis dipstick results will be summarized using categorical statistics. Clinical chemistry and hematology test results with toxicity grade 3 or higher will be listed in separate listings. Urinalysis data will be listed.

Renal impairment will be evaluated by baseline creatinine clearance (CrCL) using the Cockcroft and Gault formula (1976)

$$CrCl (mL/min) = \frac{((140 - Age) \times Weight)}{72 \times Scr} \times c$$

where:

- *Scr* is serum creatinine in (mg/dL),
- *Age* is in years (actual at baseline).
- *Weight* is in kg (at baseline),
- And where $c = 1$ for males and $c = 0.85$ for females.

Severity of renal impairment will be categorized based on CrCL at baseline (rounded to the nearest integer):

- Normal (≥ 90 mL/min)
- Mild impairment (≥ 60 to 89 mL/min)
- Moderate impairment (≥ 30 to 59 mL/min)
- Severe impairment (< 30 mL/min)

The details of data displays are presented in Appendix 9.

8.4. Vital Signs and ECG

The analyses of non-laboratory safety test results including ECGs and vital signs will be based on GSK Core Data Standards, unless otherwise specified. Summary tables will be provided for vital signs change from baseline values, and worst post-baseline vital signs results relative to baseline results. Participants with missing baseline values are assumed to have within range baseline values.

The arithmetic mean of the three recorded ECG measurements will be employed in all data summaries and participant listings. ECG measurements at baseline will be recorded, including heart rate, PR interval, QRS duration, QT interval, QRS axis and RR interval. When not entered directly on eCRF, corrected QT intervals will be calculated by Bazett's formula:

$$QTcB (msec) = \frac{QT}{\sqrt{RR/1000}}$$

and by Fridericia's formula:

$$QTcF (msec) = \frac{QT}{\sqrt[3]{RR/1000}}$$

depending on the availability of other measurements. ECGs may be collected after start of treatment, when medically warranted. In such cases, change from baseline in measurements will be derived.

Listings will be provided for baseline abnormal ECG findings, ECG values of potential clinical importance, and vital sign values of potential clinical importance. Details of the ECG values or vital signs of potential clinical importance are provided in Appendix 6. The details of data displays are presented in Appendix 9.

8.5. Classification and analysis of safety signals

As per GSK Guidance document (VQD-REF-019393), “Adverse reactions” (ARs) are undesirable effects, reasonably associated with use of a product that may occur as part of the pharmacological action of the product or may be unpredictable in its occurrence.”

Determining which AEs should be considered ARs is a two-step process:

- 1) Identification of potential ARs using quantitative methodology,
- 2) Qualitative evaluation of the potential ARs to determine if there is sufficient evidence of a causal association with the product (gepotidacin) to support inclusion in the label.

This section details the quantitative screening methods to identify potential ARs and key data displays that support quantitative identification of potential ARs and qualitative causality assessments. ARs will be reported separately from the CSR within the regulatory submission to support the safety profile of Gepotidacin.

8.5.1. Multiplicity Adjustment

As screening for potential ARs is intended as an aid to medical judgment rather than to be used for decision making, no adjustment for multiplicity will be applied.

8.5.2. Quantitative Screening for Identification of Potential ARs

Frequentist approach to screen for potential ARs will be used. Specifically, the Crowe method [Crowe B, et al, 2013] will be applied for initial screening of the large number of adverse events to generate a “short list” of potential ARs. This method is based on three measures:

- Absolute incidence rate (%) in control arm (ceftriaxone plus azithromycin),
- Estimate of treatment effect (Relative Risk [RR]) relative to active control arm (ceftriaxone plus azithromycin),
- An estimate of variability around the treatment effect (95% CI for RR).

High Level Terms (HLTs) will be used to group adverse events and the screening for potential ARs will be conducted at HLT level. Quantitative screening criteria for potential ARs endorsed by the Safety Review Team (SRT) are displayed in the following table:

Criterion	Absolute Incidence in ceftriaxone plus oral azithromycin	HLT RR (Gepotidacin vs ceftriaxone plus azithromycin)	95% CI for HLT RR*
1	No conditions	No conditions	Lower CI > 1
2	≥5%	≥1.25	No conditions
3	<5%	≥1.50	No conditions

*95% CI for RRs determined using Wald method.

For each criterion, it is necessary to have all the features described in the column headings in order for the event to be considered to have achieved that particular criterion. Events may meet more than one criterion. Events that meet at least one of the criteria are shortlisted as a potential AR.

Based on 310 participants being exposed to Gepotidacin, there is a 90% chance of observing at least one particular adverse event if the true incidence rate of that adverse event is not below 0.75%. When the active control arm has zero events, the estimate of relative risk (RR) would be undefined and therefore cannot be evaluated using the quantitative screening criteria given above. The screening criteria in this case will be based on the minimum number of subjects with the event of interest in gepotidacin arm (vs 0 in ceftriaxone plus azithromycin arm). At least 3 participants with the AE of interest must be observed in the gepotidacin arm in order to be included in the “short list” of potential ARs.

A summary table of treatment emergent adverse events by SOC, HLTs and PTs with incidence (%) for each treatment group, RR and the associated 95% CI will be generated. An additional table will be produced displaying only the adverse events meeting the pre-specified quantitative screening criteria.

The incidence of treatment emergent AEs at HLT level for each treatment group with relative risk (95% CI) will also be presented graphically. In addition to potential ARs identified using the screening criteria shown above, AESIs (specified in Section 8.2 will be automatically included in the “short list” of potential ARs.

ARs listed in the Development Core Safety Information (DCSI) for gepotidacin will be re-assessed using data from this study to determine whether they should be carried forward as ARs based on the current supporting data.

Extra care has been taken when considering labelled/known ARs, such as fungal infections and hepatobiliary disorders, for the active comparators, ceftriaxone and azithromycin. It is not known whether the investigational product, gepotidacin, may also cause the event known to be associated with the active comparator, and therefore quantitative criteria may not be met if the incidence of these ARs are similar for the investigational product, gepotidacin.

The following AEs will automatically be included in the “short list” of potential ARs for further qualitative evaluation:

- QT Prolongation: It is a very rare serious event that has been observed in early phase gepotidacin studies and therefore needs further evaluation. It is identified using HLT “ECG investigations”.
- Serious and severe adverse events: The incidence of serious and severe AEs is expected to be very low, and the qualitative assessment will be applied directly to these events without going through the quantitative screening process.
- Fungal infections: It is a known AR for ceftriaxone plus azithromycin. It is identified using HLT “Fungal infections”.
- Hepatobiliary disorders: It is a known AR for ceftriaxone plus azithromycin. It is identified using HLT “Hepatic and hepatobiliary disorders”.

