10.2. Sample Size Determination

10.2.1. Justification of Sample Size

Approximately 400 participants will be needed for the primary analysis population (i.e., the micro-ITT Population, as defined in Section 10.3) to demonstrate efficacy of gepotidacin in this study.

A conservative estimate of a 90% microbiological success rate has been assumed for ceftriaxone 500 mg IM plus azithromycin 1 g orally. Participants not returning for TOC will be considered a microbiological failure in this study.

Assuming a 90% microbiological success rate of ceftriaxone plus azithromycin and the same value for the actual success rate of gepotidacin, a sample size of 400 urogenital microbiological evaluable participants (200 participants in each treatment) will provide approximately 91% power to demonstrate noninferiority of gepotidacin and ceftriaxone plus azithromycin in adolescents and adults with uncomplicated gonorrhea caused by NG with a 0.025 one-sided significance level and a -10% noninferiority margin.

Approximately 620 participants will be enrolled and randomized 1:1 to gepotidacin and ceftriaxone plus azithromycin in order to identify approximately 400 participants that meet the definition of the micro-ITT Population.

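### The adverse-reaction screen in SAP 8.5.2 shortlists 2 gepotidacin versus 1 comparator participants but drops 2 versus 0, for terms outside its automatic-inclusion list

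*SAP*

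**What the plan says.** SAP 8.5.2 screens adverse events at HLT level against three criteria, and one is enough: "Events that meet at least one of the criteria are shortlisted as a potential AR".

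- Criterion 1: the lower 95% confidence limit for the relative risk is above 1.
- Criterion 2: control incidence is 5% or more and the relative risk is at least 1.25.
- Criterion 3: control incidence is below 5% and the relative risk is at least 1.50.

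Criteria 2 and 3 carry no confidence-interval condition, and no criterion sets a minimum count.

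A separate paragraph covers a comparator arm without events. It opens with a detection statement: "Based on 310 participants being exposed to Gepotidacin, there is a 90% chance of observing at least one particular adverse event", for a true incidence not below 0.75%. It then explains why another rule is needed: "When the active control arm has zero events, the estimate of relative risk (RR) would be undefined". The rule is: "At least 3 participants with the AE of interest must be observed in the gepotidacin arm".

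The section goes on to list events that skip the count rule. Adverse events of special interest, QT prolongation, fungal infections and hepatobiliary disorders join the short list automatically. Serious and severe events go straight to qualitative assessment. Under SAP 8.5.3 the causality displays are produced for the events on the short list.

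**The concern.** A screen of this kind should never become harder to pass when a comparator event is taken away and the gepotidacin count is unchanged. This one does. With two gepotidacin participants, a term is shortlisted if one comparator participant also had the event, and dropped if none did.

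The short list decides which terms get the causality displays, so a term seen in two gepotidacin participants and in no comparator participant can miss a review that a weaker contrast would receive.

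The paragraph also gives no detection probability for the three-participant threshold. Its only figure concerns seeing one event, and one event does not shortlist a term when the comparator has none.

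**Working it through.** **Inputs.** SAP 8.5.2 gives 310 participants exposed to gepotidacin, a reference incidence of 0.75%, the three criteria and the threshold of 3. Protocol 10.2.1 gives the allocation: "Approximately 620 participants will be enrolled and randomized 1:1 to gepotidacin and ceftriaxone plus azithromycin". I therefore take 310 per arm. All counts are participants with the event.

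**The SAP's own figure.** With X ~ Binomial(310, 0.0075):

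- P(X = 0) = 0.9925^310 = 0.0969
- P(X ≥ 1) = 1 − 0.0969 = 0.9031

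This reproduces the stated 90%. The incidence that gives exactly 90% is 1 − 0.1^(1/310) = 0.740%.

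**Smallest gepotidacin count that is shortlisted.** With equal arms the relative risk is the ratio of counts, so criterion 3 needs a gepotidacin count of at least 1.5 times the comparator count.

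| Comparator participants | Rule that applies | Smallest gepotidacin count |
|---|---|---|
| 0 | zero-comparator rule | 3 |
| 1 | criterion 3 (≥ 1.5) | 2 |
| 2 | criterion 3 (≥ 3.0) | 3 |
| 3 | criterion 3 (≥ 4.5) | 5 |

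The first row breaks the order. For 2 versus 1, control incidence is 1/310 = 0.32%, the relative risk is 2.00 and the Wald 95% interval is 0.18 to 21.9. Criterion 3 is met. For 2 versus 0, the relative risk is undefined and 2 is below 3, so the term is dropped.

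The 2 versus 1 result does not depend on exact balance: the relative risk runs from 1.88 (320 gepotidacin, 300 comparator) to 2.13 (300 and 320). The 3 versus 2 case sits exactly on 1.50 with equal arms, so slight imbalance could move it either way.

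**Chance of reaching the zero-comparator threshold at 0.75%.** With P(X = 1) = 0.2271 and P(X = 2) = 0.2651:

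- P(X ≥ 2) = 1 − 0.0969 − 0.2271 = 0.676
- P(X ≥ 3) = 0.676 − 0.2651 = 0.411

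Solving the same tail for 90% gives a true incidence of about 1.25% for 2 participants and 1.71% for 3.

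**Full rule.** I summed the joint binomial probability over all pairs of counts that are shortlisted. Gepotidacin incidence is 0.75%, with 310 per arm; the comparator rates are assumptions.

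| True comparator rate | Shortlisted, threshold 3 | Shortlisted, threshold 2 |
|---|---|---|
| 0 | 41% | 68% |
| 0.1% | 47% | 66% |
| 0.25% | 49% | 61% |

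Under the current rule, an event that occurs only on gepotidacin is less likely to be flagged than one that also occurs on the comparator. A threshold of 2 restores the expected order.

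**Cost when there is no drug effect.** Moving from 3 to 2 adds exactly the 2 versus 0 outcome, with probability C(310,2) p² (1 − p)^308 × (1 − p)^310 when both arms share a true rate p (assumed).

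- p = 0.1%: 0.0352 × 0.7333 = 2.6%, so shortlisting rises from 1.2% to 3.8% per HLT.
- p = 0.2%: 0.1034 × 0.5376 = 5.6%, so it rises from 5.9% to 11.5% per HLT.

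**The case against.** Four points can be made in the plan's defense.

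First, a reader might infer that the 90% figure is an arithmetic error, or that the SAP offers it as the sensitivity of the screen. The documents support neither. The sentence states the chance of at least one event, it is right for that, and the SAP never calls it the performance of the three-participant rule. The 41% answers a different question and does not correct the 90%. What stands is that the adopted threshold has no detection figure of its own.

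Second, a reader might infer that rare events seen only on gepotidacin generally escape causality review. That goes too far. Serious and severe events are assessed whatever their count. So are QT prolongation, fungal and hepatobiliary terms, and all events of special interest, which under SAP 8.2 include the whole gastrointestinal system organ class. Reactions already in the development core safety information are re-assessed separately. The gap covers the remaining terms, and only at exactly 2 versus 0.

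Third, nothing is hidden. SAP 8.5.1 describes the screening as an aid to medical judgment, and every treatment-emergent event is tabulated by HLT and arm, so a 2 versus 0 term stays visible. This stands and limits the severity. It does not explain why the test is stricter where the contrast is larger.

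Fourth, consistency could also be restored by requiring at least 3 gepotidacin participants under criterion 3, and the threshold of 3 may come from the cited screening method, which cannot be checked here. That is a fair alternative, but it gains order by giving up sensitivity, which suits a first-pass aid to judgment less well. Lowering the threshold has its own price: chance shortlisting roughly doubles or triples at the rates shown above.

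**Conclusion.** The inconsistency is real and follows from the text alone: for terms outside the automatic-inclusion list, 2 versus 1 is shortlisted and 2 versus 0 is not. With the comparator rate at zero, a term with 0.75% incidence on gepotidacin reaches the current threshold 41% of the time; with a threshold of 2 it would be 68%.

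The binomial figures assume 310 per arm and independent participants. They equal the probability of shortlisting only if the comparator has no events; the full-rule figures rest on assumed comparator rates.

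This is a minor consistency correction to an advisory safety screen. SAP 8.5 reports adverse reactions separately from the clinical study report, and no efficacy conclusion depends on them.

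**What to change.** In SAP 8.5.2, change the zero-comparator rule to at least 2 gepotidacin participants, the smallest count already shortlisted against one comparator participant.

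Keep the 90% sentence, which is correct, and add one for the threshold: when the comparator has no events, the chance of reaching 2 gepotidacin participants among 310 is 68% at a true incidence of 0.75%, and a 90% chance needs about 1.25%. If the threshold of 3 is kept, give the reason for it and quote 41% and 1.71% instead. In either case keep the condition that the comparator has no events, because the figures are not general shortlisting probabilities.

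The change is a few lines of SAP text and one programming condition. Its running cost is the extra chance shortlisting quantified above, which falls on the qualitative review.

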8.5.3. Qualitative Causality Assessment

After identification of potential ARs using the quantitative method, qualitative evaluation of the potential ARs in the “short list” will be performed to determine if there is sufficient evidence of causal association with gepotidacin. The following data displays will be produced for each AE in the “short list” of potential ARs to support the qualitative causality assessments.

- Summary of treatment emergent adverse events by SOC, HLT and PTs by subgroups (Consistency check between subgroups: Actual Age Category, Sex, Race, Renal Impairment Evaluated by Baseline CrCL, Geographic Region and HIV Status)
- Incidence rate of treatment emergent AEs according to different attributes by treatment group (Consistency check in AE attribute: AEs related to study treatment, AEs leading to permanent discontinuation of study treatment, AE leading to dose reduction, AE leading to dose interruption/delay, SAEs related to study treatment, Fatal SAEs, and Fatal SAEs related to study treatment)
- Summary of treatment emergent AEs by HLT and Maximum Grade (Consistency check in AE attribute)
- Summary of Cumulative Incidence of Treatment Emergent Adverse Events (HLTs) by Time to First Occurrence (Temporal association)
- Heatmap of RR for treatment emergent AE HLTs that meet the screening criteria by SOC (Consistency check in AE attribute: AEs, Drug-related AEs, SAEs, AEs leading to discontinuation of study treatment, and Grade 3 or Higher AEs)
- Kaplan Meier Curve for Treatment Emergent Potential AR Event by Treatment (Temporal association)

Additional data displays may be generated as needed to assist with further qualitative assessment of the potential ARs once the safety data is reviewed. The generated data displays may be useful in evaluating the likelihood of a causal association and the strength of causality by assessing the following factors:

- Consistency across pre-defined subgroups,
- Consistency according to clinically relevant attributes,
- Temporal association.

9. ADDITIONAL ANALYSES DUE TO THE COVID-19 PANDEMIC

9.1. Study Population

9.1.1. Participant Disposition

A summary of recruitment by country and site, relative to COVID-19 pandemic measures will be produced. For details on the determination of phases of the COVID-19 pandemic measures see Appendix 2. A country level listing of the dates of the COVID-19 Pandemic measures will be produced.

9.1.2. Protocol Deviations

An optional participant listing of significant protocol deviations related to COVID-19 may be produced, however, these deviations will already be captured in the listing of all significant protocol deviations. Visits and assessments missed due to the COVID-19 pandemic, together with visits conducted remotely, will be summarized in both a table and listed by participant.

9.2. Safety

COVID-19 assessments and symptom assessments for participants with COVID-19 AEs will be listed, which will include the clinical outcome of any COVID-19 AE.

10. BENEFIT/RISK

Forest plots showing the treatment effect and confidence intervals related to benefits and risks of treatment with gepotidacin will be created. Benefits will be represented by risk differences and corresponding confidence intervals from the following analyses based on the Micro-ITT analysis population:

- Microbiological outcome and response rate of urogenital Gonorrhea at the TOC Visit (primary analysis),
- NAAT outcome and response rate of urogenital Gonorrhea at the TOC Visit (exploratory analysis).

For these analyses, risk differences and 95% confidence intervals will be determined using the methods described in Section 7.1.6.1 and Section 7.3.1.5, respectively. Additionally, relative risks and corresponding 95% confidence intervals will be displayed for the following safety endpoints: incidence of AEs, SAEs and, separately, CV, GI, *C. difficile*, and AChE-I AESIs using the Safety analysis population. Confidence intervals for relative risks will be determined using the asymptotic Wald method.

